Cardiff

[name]

Email: [contact]

[contact]

[name]

Managing Director and CEO of shift.ms

[name]

Email: [contact]

[contact]

ii. LIST of CONTENTS

GE	NERAL INFORMATION	Page No.
TIT	LE PAGE	1
RE	SEARCH REFERENCE NUMBERS	2
SIG	SNATURE PAGE	3
I. K	EY TRIAL CONTACTS	4
II. L	IST OF CONTENTS	6
III.	LIST OF ABBREVIATIONS	7
IV.	TRIAL SUMMARY	8
V. F	FUNDING AND SUPPORT IN KIND	9
VI.	TRIAL FLOW CHART	12
1	BACKGROUND	13
2	RATIONALE	15
3	OBJECTIVES AND OUTCOME MEASURES/ENDPOINTS	17
4	TRIAL DESIGN	18
5	TRIAL SETTING	21
6	PARTICIPANT ELIGIBILITY CRITERIA	21
7	TRIAL PROCEDURES	22
8	STATISTICS AND DATA ANALYSIS	31
9	DATA MANAGEMENT	32
10	MONITORING, AUDIT & INSPECTION	33
11	ETHICAL AND REGULATORY CONSIDERATIONS	34
12	DISSEMINIATION POLICY	38
13	REFERENCES	39

iii. LIST OF ABBREVIATIONS

Define all unusual or 'technical' terms related to the trial. Add or delete as appropriate to your trial. Maintain alphabetical order for ease of reference.

ACT Acceptance and Commitment Therapy

CI Chief Investigator

GCP Good Clinical Practice

GDPR General Data Protection Regulation

HCP Healthcare Professional ICF Informed Consent Form

IRAS Integrated research application system

ISF Investigator Site File
MS Multiple Sclerosis

MSIS-29 Multiple Sclerosis Impact Scale (29 items)
MS-WIS Multiple Sclerosis Work Instability Scale

MPFI Multidimensional Psychological Flexibility Index
NFI-MS Neurological Fatigue Index for Multiple Sclerosis

NHS National Health Services
PF Psychological Flexibility
PI Principal Investigator

PIS Participant Information Sheet
PPI Patient and Public Involvement
PwMS People with multiple sclerosis
READY(for MS) Resilience for Adults Everyday
REC Research and ethics committee
R&D Research and development

SE Self-efficacy

SUS System useability scale

TMF Trial Master File

TMG Trial Management Group
TSC Trial Steering Committee

USE-MS Uni-dimensional Self-efficacy Scale for Multiple Sclerosis

VAS Visual Analogue Scale

WI Work Instability

iv. TRIAL SUMMARY

Trial Title	Assessing NHS ImplemeNTation of an onlinE Resilience-training Acceptance and Commitment Therapy (ACT) programme to prevent job loss in MS			
Internal ref. no. (or short title)	INTERACT-MS			
Trial Design	Hybrid Feasibility-Implementation Trial			
Trial Participants	(1) MS Healthcare Professionals (2) People with Multiple Sclerosis (in employment)		
Planned Sample Size	(1) 50 (2) 250			
Treatment duration	12 weeks			
Follow up duration	6 months			
Planned Trial Period	42 months			
Research Aim(s) and Objectives	programme to PwMS following (2) The effectiveness of delivering for PwMS when supported by treem outcomes	ed with PwMS 'REsilience and ') resource to support PwMS s of training MS health practitioners out delivery of the digital READY an immersive training programme. The READY programme in the NHS rained MS practitioners and the long-low MS practitioners support/engage and programme? Tow PwMS engage with the READY outcomes		
	Primary Outcomes	Secondary Outcomes		
Outcome measures	Work Instability (MS-WIS)	User Satisfaction (SUS)		
	Psychological Flexibility (MPFI)	Mood (HADS)		
	Resilience (R-15)	Impact of MS (MSIS-29)		
	Self-efficacy (USE-MS)	Qualitative data		

v. FUNDING AND SUPPORT IN KIND

FUNDER(S) (Names and contact details of ALL organisations providing funding and/or support in kind for this trial)	FINANCIAL AND NON FINANCIALSUPPORT GIVEN
MS Society	Total: £211,757.34
MS National Centre	Salaries: £195,229.55
[name]	Consumables: £11,347.79
[name]	Equipment: £180.00
	Conferences: £4,000.00
Leeds Teaching Hospitals NHS Trust	Study site, provision of premises for study
[name],	participant visits and assessments
Leeds	
[name]	

v. ROLE OF TRIAL SPONSOR AND FUNDER

The study SPONSOR is Leeds Teaching Hospitals NHS Trust and it will provide premises for carrying out study specific activity that involves patients. As the NHS trust is the sponsor for the study, the NHS indemnity scheme will cover the study specific activity that takes place on trust premises. The sponsor has no role in the development or design of the protocol but will have reviewed the protocol and provided its approval prior to any study specific activity commences. The outcomes of the study will be made known to the sponsor and the sponsor will be acknowledged in any publications arising from the study.

The FUNDER is the UK MS Society. The outcomes of the study will be made known to the funder and the funder will be acknowledged in any publications arising from the study. Terms and conditions of the Award are provided in Appendix A.

vi. ROLES AND RESPONSIBILITIES OF TRIAL MANAGEMENT COMMITEES/GROUPS

& INDIVIDUALS

Trial Management Committees

Trial Management Group (TMG)

The TMG will meet at regular intervals to ensure all practical details of the trial are progressing well and working well and everyone within the trial understands them.

Enrolment of NHS MS Centres **Refinement of Digital READY** Ethical Approvals & Digital READY is a web-based resilience training programme for Multiple Sclerosis Governance Enrolment of health professionals (HCPs) in MS (n=50) Digital introductory workshop delivered with Psychologist Outcome Measures: Pre-READY questionnaire (Baseline Psychological Flexibility; Qualitative feedback) HCPs complete Digital READY and training (n=50, 5 HCPs per site) 2a. Digital READY participation Week 3 interval support call (delivered by Psychologist) Development of troubleshooting toolkit Outcome Measures: Psychologist notes on troubleshooting, Post-intervention questionnaire pack (Psychological flexibility, User satisfaction) and 6m follow up questionnaire (Psychological flexibility) 2b. READY training workshop (delivered by Psychologist/Project manager) Outcome Measures: Knowledge/competencies test, qualitative feedback questionnaire Sub-set: Semi-structured audio-recorded research interviews post-READY **Enrolment of PwMS** (n=250; 5 per HCP, 25 per site) Screening: Employment status, MS-WIS (Work Instability), Consent to take part Outcome Measures: Pre-READY questionnaire (Baseline Psychological Flexibility, Work Instability, other psychological factors) **PwMS complete Digital READY** Digital READY participation Week 3 interval support call (delivered by HCP) Outcome Measures: HCP notes on troubleshooting, Post-intervention and 6m follow up questionnaire packs (Psychological flexibility, Work Instability, User satisfaction, other psychological factors) Sub-set: Semi-structured audio-recorded research interviews post-intervention and 6m Analysis and write up Primary outcomes: PWMS MS-WIS at 6m, PWMS Psychological flexibility at 6m, HCP Competency/Knowledge test

Secondary outcomes: HCP Psychological flexibility at 6M

Process evaluation: Qualitative interviews, notes and questionnaire responses

1 BACKGROUND

Multiple Sclerosis (MS) is commonly diagnosed between the ages of 20-40¹, a key life stage for working and during which career milestones tend to occur. Despite the majority of PwMS being in work at time of diagnosis, up to 80% have left work within 10-15 years^{2,3}. PwMS are less likely to be in paid employment compared with the general population⁴ and even compared with other chronic conditions⁵. These correlates occur even where there is low physical and cognitive impact⁶ suggesting that psychological barriers and fatigue may be key barriers to job retention^{7,8}.

Low mood and self-efficacy are associated with reduced work participation and declining work performance in PwMS^{7,9,10}. Perceived lack of support and stigmatisation can also lead to negative work outcomes for PwMS^{11,12}. However, over half of PwMS not in paid work report that they "ideally, would like to work"¹³. In addition to financial security, paid employment offers psychological benefits including improved quality of life¹⁴ and self-confidence¹⁵. PwMS who stay in work also report lower symptom incidence¹⁶.

A validated scale for PwMS developed at Leeds can measure and help screen for the risk of job loss (MS Work Instability Scale (MS-WIS)¹⁷). Previous research using this scale has linked risk of job loss to psychological factors such as self-efficacy⁷. An on-going study at Leeds (MS Proactive) has shown that PwMS with lower psychological flexibility tend to have higher work instability (WI; i.e. risk of job loss).

Psychological flexibility, closely linked to resiliency, is the cornerstone of mental health¹⁸ and refers to the ability to effectively manage unwanted inner experiences (e.g., thoughts, memories, bodily sensations) in the present, while adjusting behaviors in the context of changing situational demands to ensure one is behaving consistently with personal values^{19,20}.

A review of psychological interventions for PwMS found a positive impact for both physical and psychological outcomes, including fatigue²¹. One type of psychological intervention called acceptance and commitment therapy (ACT) is an approach underpinned by the psychological flexibility framework. ACT has been shown to significantly improve self-efficacy as well as pain acceptance, low mood and anxiety²².

Increasing self-efficacy can also offer protective factors against illness invalidation experiences^{22, 23}. Illness invalidation in invisible illnesses can lead to negative work outcomes, which may further contribute to withdrawing from work early²⁴. Further, the increased psychological flexibility from ACT interventions can play a positive mediating role in organisational wellbeing²⁵.

A team in Australia have developed an ACT-based programme for PwMS called 'REsilience and Activities for every DaY'²⁶ (READY). Researchers at Leeds have recently co-developed with PwMS a UK online version called 'READY for MS'. This online programme can be used

on a computer or mobile device from home or while commuting, thus reducing the need to take further time off work to visit a psychologist.

There is often a gap in uptake of evidence-based psychological interventions²⁷. One way to address this is by training health professionals in the delivery of such interventions. In order to check that the intervention can be delivered and supported by health professionals as intended, we need to test it in its proposed setting. This is known as assessing 'intervention fidelity' and can help to provide empirical evidence to support the implementation of an intervention.

In a recent Italian study, psychologists trained to deliver the group-version READY programme experienced personal and professional benefits such as resilience, ACT skills development, and a reduced vulnerability to burnout²⁸. Training health professionals to support the UK digital READY may therefore have a positive impact on wellbeing for the health professionals receiving this training. This is particularly timely, as a recent study has reported that burnout among MS healthcare professionals increases the risk of sickness absence²⁹. Furthermore, our online READY programme is predominantly self-guided with supplementary support from a facilitator. It therefore offers an intervention option that should not add significant burden to the healthcare professional workload.

Psychological support services in the UK are under significant strain with 1.6 million people reported to be on NHS waiting lists for specialised mental health support³⁰. The UK Household Longitudinal Study³¹ reported that psychological wellbeing in the UK has significantly worsened following the Covid-19 pandemic, further increasing the need for accessible psychological interventions. Psychological flexibility offers protective factors that mimimise the adverse mental health impacts of Covid-19³². In the UK, PwMS are more likely to be in regular contact with a MS nurse, occupational therapist, or physiotherapist than a neuro-psychologist. Therefore, training these health professionals to deliver and support this programme may improve access to psychological interventions for PwMS who would benefit from them.

Socio-economic status further impacts work opportunities for PwMS³³ and so developing interventions should consider accessibility to all socio-economic groups. Qualitative work throughout this research project will seek to engage with multiple MS communities, especially marginalised groups, to identify barriers to such interventions.

While this study will focus on the impact of risk of job loss for PwMS, previous versions of the READY programme have been shown to improve a range of psychological factors that influence quality of life in MS³⁴. Therefore, successful implementation of this programme by healthcare professionals could lead to wider use of this programme for PwMS in a range of settings who may benefit from resilience-training interventions.

2 RATIONALE

PwMS are disproportionately leaving work early^{4, 35}. Previous research has shown that psychological factors play a key role in this⁷. However, in the UK, psychological services are under significant strain with 1.6 million people reported to be on NHS waiting lists for specialised mental health support³⁰. Psychological wellbeing in the UK has significantly worsened following the Covid-19 pandemic³¹, further increasing the need for accessible psychological interventions.

Psychological flexibility offers protective factors that minimise the adverse mental health impacts of Covid-19³² There is often a gap in uptake of evidence-based psychological interventions³⁶. One way to address this is by training health professionals in the delivery of such interventions. An Italian study trialled a training programme for psychologists to deliver the group-version READY programme and found it can lead to personal and professional benefits for these health professionals³⁷. Training health professionals to support the UK digital READY programme may improve access to psychological interventions for PwMS who would benefit from them.

In the UK, PwMS are more likely to be in regular contact with an MS nurse, occupational therapist, or physiotherapist than a neuropsychologist. Therefore, training these MS health professionals may offer greater access to the READY programme. MS nurses, occupational therapists, and physiotherapists may also be able to offer more personalised support as part of the digital READY programme. ACT interventions have been shown to protect against burnout, which may be particularly relevant in the wake of the Covid-19 pandemic.

The Italian study found that healthcare professionals who engaged in the READY programme as part of training to deliver it benefitted from this increase in psychological flexibility²⁸. Therefore, training health professionals to support digital READY may increase their capacity to continue working, further benefitting PwMS who seek support from them.

It is important to test whether the READY intervention can be plausibly implemented in an NHS or community healthcare setting. If there are barriers to using this intervention in this setting, there is unlikely to be significant uptake and therefore the intervention cannot reliably benefit PwMS. Assessing the effectiveness of integrating an intervention option that can be supported by healthcare professionals in a way that reduces rather than increases long-term burden is also important. Giovannetti et al³⁷ found that where health professionals were supported to undertake and deliver a group-based READY programme, beneficial outcomes included resilience, ACT skills development, and reduced vulnerability to burnout.

The integrated process evaluation allows us to assess in-depth what will work and what might need to be adjusted prior to investing time and resources to a large-scale randomised control trial (RCT). While this study will focus primarily on the impact of risk of job loss for PwMS, previous versions of the READY programme have been shown to improve a range of

psychological factors that influence quality of life in MS³⁴. Therefore, successful implementation of this programme by healthcare professionals could lead to wider use of this programme for PwMS in a range of settings who may benefit from resilience-training interventions.

2.1 Assessment and management of risk

PwMS who are excluded at screening due to having low work instability may feel disappointed at not being able to participate in the trial. We will explain that the trial is looking at the effectiveness of the READY programme for PwMS who report work instability, whereas it would be difficult to measure a meaningful improvement if work instability is already low.

The READY for MS digital programme asks participants to think about and reflect on thoughts that may be psychologically difficult or distressing. The PIS will include contact information for the research team as well as where to find additional support. Participants will receive a checkin phone call with the opportunity to raise and discuss any further support needed. If a safeguarding concern is identified, site specific safeguarding protocols will be followed.

The benefit of participating in the study is that this research addresses one of the key priorities of the MS Society in improving self-management of MS.

Training health professionals to support the UK digital READY may have a positive impact on wellbeing for the health professionals receiving this training. The online READY programme is predominantly self-guided with supplementary support from a facilitator. It therefore offers an intervention option that should not add significant burden to the healthcare professional workload. In the UK, PwMS are more likely to be in regular contact with a MS nurse, occupational therapist, or physiotherapist than a neuro-psychologist. Therefore, training these health professionals to deliver and support this programme may improve access to psychological interventions for PwMS who would benefit from them.

Participants will be informed of their right to withdraw from the study at any time, without the need to give a reason. Participants' consent to continue participation will be re-confirmed at research contact points, such as research data collection (questionnaires).

3 OBJECTIVES AND OUTCOME MEASURES/ENDPOINTS

3.1 Aim/s and Objectives

A digital resilience-training programme called 'READY for MS' has been co-developed in the UK and piloted with PwMS who report work instability. It is important to assess that the digital UK READY for MS programme can be delivered and received as intended; this is known as "Intervention fidelity". Specifically, this study aims to monitor fidelity to function, i.e. measuring the core functions of the READY for MS programme, through psychological self-report measures. This is important for checking (validating) the use of READY for MS in a "real world" setting. To do this, we will train MS healthcare professionals to support the delivery of READY for MS and then check whether it has been delivered and received as intended. We will also check that READY leads to the intended long-term outcomes for PwMS who receive it.

Aim: To assess NHS implementation of an online type of Acceptance and Commitment Therapy (ACT) codeveloped with PwMS 'REsilience and Activities for every DaY for MS' (READY) resource to support resilience at work for PwMS.

This will be delivered through five objectives:

- 1. The feasibility and effectiveness of training MS health practitioners in several NHS centres to support delivery of the digital READY programme to PwMS following an immersive training programme.
- 2. The effectiveness of delivering the READY programme in the NHS for PwMS when supported by trained MS practitioners and the long-term outcomes
- 3. Which/how contexts influence how MS practitioners support/engage with PwMS completing the READY programme?
- 4. Which/how contexts influence how PwMS engage with the READY programme and the long-term outcomes
- 5. To what extent intervention fidelity mediates these long-term outcomes

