3.2 Primary endpoint/outcome

The primary quantitative outcome measures for this study will be work instability, as measured by the MS Work Instability scale, resilience, psychological flexibility, and self-efficacy. We want to check that the digital READY programme will continue to work as

intended when supported by trained healthcare professionals, therefore we would expect to see a psychological benefit for PwMS being supported to use the READY programme in an NHS setting.

We expect that this ACT-based programme should lead to increased resilience, psychological flexibility, and self-efficacy. We theorise that increasing these psychological factors should lead to a reduction in work instability. This should mean we see a significant reduction in work instability in participants who complete the digital READY for MS programme.

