4 TRIAL DESIGN

This study is a hybrid effectiveness-implementation trial, by which we are simultaneously trialling the effectiveness of an intervention but also exploring its implementation. We will focus on 'fidelity to function', meaning that the intervention still delivers the expected outcomes, while recognising that local adaptation is vital for any intervention to work because every setting and site is different.

We will use purposive sampling for this study, which means we will actively seek to include representatives of different demographic and socio-economic backgrounds.

The trial will include the following phases:

Phase 1: Programme refinement

Findings from the recent co-production and pilot study (MS PROACTIVE) will be utilised to refine and further develop the digital READY programme. The digital programme consists of an introductory module, 6 core modules on ACT factors (Mindfulness, Acceptance, Defusion, Observer Self, Values/Meaningful action, and Future Planning) then a final booster module to be completed after a 5-week break. Aside from the booster module, it is recommended to complete one module per week and each module takes around 40 minutes to complete. There are additional exercises that participants can complete under their own initiative between modules, with accompanying guided audio-recordings (e.g. Mindfulness of the breath). A workbook accompanies the digital content, with reflective written exercises for participants to complete during and between modules. This workbook forms a personal plan that participants can refer back to on completion of the programme.

Phase 2: Getting HCPs READY

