T1/Week 3: The HCP will conduct an interval support call with HCPs between weeks 2-4 of completing the programme. HCPs will be encouraged to record notes from these support calls to contribute to lightning reports and the overarching process evaluation

T2/Week 8: Participants will be invited to complete follow-up questionnaire packs at week 8 from baseline. The questionnaire packs will be available to be completed digitally and will collect demographic information to include:

- Employment status
- Employment contract type
- Household income
- Number of sick days taken in last 6 months
- Relapse occurring in last 6 months
- Anchor VAS question on general health rating
- Validated self-report scales for Work Instability (MS-WIS), Resilience (CD-RISC-10), Psychological Flexibility (MFPI), Self-efficacy (USE-MS), Mood (HADS), and Impact of MS (MSIS-29) and User Satisfaction (SUS; see Table 1)

T3/Month 6: Participants will be invited to complete a further follow-up questionnaire pack at month 6 from baseline. The questionnaire packs will be available to be completed digitally and will collect demographic information to include:

- Employment status
- Employment contract type
- Household income
- Number of sick days taken in last 6 months
- Relapse occurring in last 6 months
- Anchor VAS question on general health rating
- Validated self-report scales for Work Instability (MS-WIS), Resilience (CD-RISC-10), Psychological Flexibility (MFPI), Self-efficacy (USE-MS), Mood (HADS), and Impact of MS (MSIS-29) and User Satisfaction (SUS; see Table 1)

.

Table 3 - Schedule of procedures (Phase 3: PwMS)

Phase 3: PwMS	T-2	T-1	T0	T1	T2	T3
	Approach	Screening	Baseline	Week 3	Week 8	Month 6
		(≥24h)	(Pre- READY)	(± 7 days)	(Post- READY)	
PIS given	Х					
Consent		Х				
Screening		Х				
Baseline Demographics - Date of birth - Sex - Confirmed MS diagnosis and subtype - Year of MS onset/ diagnosis - Gender identity - Ethnicity			Х			
MS History - MS subtype - Confirmed relapse(s) (last 6 months) - DMT status			X		Х	Х
 Employment demographics Employment status Employment contract type Household income Number of sick days (last 6 months) 			x			
General health VAS			Х		Х	Х
Multiple Sclerosis Work Instability Scale (MS-WIS)		Х	Х			
Connor-Davidson Resilience Scale (CD-RISC-10)			Х		Х	Х
Multi-dimensional Psychological Flexibility Inventory (MFPI)			Х		Х	Х
Unidimensional Self-efficacy scale for MS (USE-MS)			Х		Х	Х
Hospital Anxiety and Depression Scale (HADS)			X		X	Х

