Multiple Sclerosis Impact Scale (MSIS-29)			Х		Х	Х
System Useability Scale (SUS)					Х	Х
Qualitative: Interval support contact notes				Х		
Qualitative: Semi-structured interviews					Х	Х

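### Objective 5 treats fidelity as a mediator, but fidelity is measured by scales that are also primary outcomes, and no quantitative per-person measure of READY use or delivery is scheduled for PwMS

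*Protocol*

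**What the plan says.** Section 3.1 first describes fidelity in general terms, as the programme reaching people and being taken up in the way it was meant to. It then narrows what the study will monitor to fidelity to function, that is, "measuring the core functions of the READY for MS programme, through psychological self-report measures". Section 4 explains fidelity to function as "meaning that the intervention still delivers the expected outcomes". Objective 5 asks "To what extent intervention fidelity mediates these long-term outcomes".

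Section 3.2 gives the primary quantitative outcomes as "work instability, as measured by the MS Work Instability scale, resilience, psychological flexibility, and self-efficacy". It expects a significant fall in work instability "in participants who complete the digital READY for MS programme".

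For PwMS, the text of Section 7.4 and Table 3 schedule the outcome scales, the usability scale (SUS), one set of week-3 call records listed as "Qualitative: Interval support contact notes", and interviews in a subset. On those call records Section 7.4 says "HCPs will be encouraged to record notes from these support calls", whereas Section 4 states that HCPs will record them. Section 7.6 adds free-text pulse questionnaires every two weeks. Section 9.1 lists three data sources: questionnaires, medical records and qualitative data. Section 8.2 examines whether changes in the outcome scales are linked and names no fidelity variable.

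**The concern.** A mediator has to be something other than the outcome it is meant to explain. Here the working definition of fidelity draws on the same family of scales that count as primary outcomes, and Section 4 comes close to saying that fidelity is present when the outcomes are good. The general definition in Section 3.1 avoids this, but nothing quantitative is scheduled in PwMS to measure it.

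The practical loss is in interpretation. Section 2 presents the study as a way to learn what works and what needs adjusting before a large randomised trial. If work instability does not fall, the team will want to know whether participants did not use READY or used it without benefit. With no per-person figure for use, the numerical data cannot tell these apart. If work instability does fall, Objective 5 could be reported as answered when only the link between psychological change and work instability had been examined.

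**Working it through.** **1. The plan's own figure.** Section 8.1 wants 200 cases after 20% attrition: 200 / (1 − 0.20) = 250, as stated. Ten sites × 25 and 50 HCPs × 5 also give 250. Nothing below alters this.

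**2. Overlap of mediator and outcome.** Section 3.1 does not name the scales that measure fidelity. I take them to be those for the three psychological factors that Section 3.2 expects READY to raise.

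- Resilience (CD-RISC-10): fidelity measure and primary outcome.
- Psychological flexibility (MPFI): fidelity measure and primary outcome.
- Self-efficacy (USE-MS): fidelity measure and primary outcome.
- Work instability (MS-WIS): primary outcome only, unless Section 4's wording is read literally.

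The overlap is 3 of 4 primary outcomes on Section 3.2's list. The flow chart's shorter list names only psychological flexibility among the three, so one scale overlaps there.

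**3. What is scheduled in PwMS that bears on delivery or use.**

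- Week-3 call notes: per person, free text, classed as qualitative and assigned to the process evaluation in Section 4.
- Pulse questionnaires: free text on what is and is not going well.
- Interviews: a subset; Section 11.3 gives 10 PwMS.
- SUS: numerical and per person, but it rates usability or satisfaction, not use.
- HCP competency test (Table 2): numerical, but one score per HCP. Fifty scores would be shared among 250 participants, five to a score, and they reflect training rather than what each person received.

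Scheduled numerical per-person measures of modules done or call held: 0.

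**4. Can returning the T2 pack stand for completion?** Section 4 describes an introductory module, 6 core modules and a booster after a 5-week break: 1 + 6 + 1 = 8 modules. At one a week the first seven take 7 weeks, and the booster falls at about 7 + 5 = 12 weeks, which agrees with the 12-week treatment duration in the summary. Section 7.4 sends the T2 pack at week 8 from baseline, before the booster. Section 4 ties the pack to finishing the programme, but no item records that this happened. Returning the pack therefore does not identify completers.

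**5. Why the overlap matters (illustration, not a planned analysis).** Suppose one scale is measured at baseline, week 8 and month 6 with equal variances and a common correlation ρ between occasions, and there is no intervention effect and no difference in delivery. Setting the variance to 1:

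- covariance of the two changes from baseline = ρ − ρ − ρ + 1 = 1 − ρ
- variance of each change = 2(1 − ρ)
- correlation = (1 − ρ) / [2(1 − ρ)] = 0.50 for any ρ below 1

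Adjusting for baseline instead, the partial correlation of week 8 with month 6 is (ρ − ρ²)/(1 − ρ²):

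- ρ = 0.5: 0.25/0.75 = 0.33
- ρ = 0.7: 0.21/0.51 = 0.41
- ρ = 0.8: 0.16/0.36 = 0.44

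In 4,000 simulated trials of 200 people at each of these values of ρ, the correlation of changes averaged about 0.50 and was significant every time. A separately recorded count of 0 to 8 modules with no effect gave a correlation of about 0 and was significant in about 5%. The values of ρ and the distribution of the count are assumptions.

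**The case against.** A reader might infer that Objective 5 is circular throughout and cannot be answered. The protocol does not support that. Section 3.2 sets out a causal order in which psychological factors improve and work instability then falls. MS-WIS is a different scale, and Section 7.4 collects the psychological scales at week 8, before month 6. Section 8.2 broadly plans to examine that link. Whether week-8 change in flexibility or resilience predicts month-6 MS-WIS is a coherent question. It tests mechanism, however, and does not show whether READY was delivered and received as meant.

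A reader might also infer that a positive result is built in. The illustration pairs a scale with itself, and Section 8.2 does not specify that pairing. It shows a hazard for the three overlapping outcomes and says nothing about the flexibility-to-MS-WIS relation.

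Nor are the call notes the only information on delivery. The competency test, pulse questionnaires and interviews are scheduled, and the process evaluation will address use and barriers qualitatively. This stands, so the gap is limited to quantitative per-person data.

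Fidelity to function was a deliberate choice, because Section 4 holds that sites must adapt locally. That is a fair reason not to judge sites by rigid adherence, but it does not remove the need to know who used the programme. A platform log may exist without having a row in a visit table, but Section 9.1 does not list one. Finally, a module count is self-selected and confounded by motivation and health, so it would not identify mediation either. That is why the remedy asks for association only.

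**Conclusion.** The point holds within these limits. For three of the four primary outcomes in Section 3.2, the mediator in Objective 5 is not distinct from the outcome. For MS-WIS, the scheduled data can address mechanism but not fidelity. No quantitative per-person measure of use or delivery is scheduled for PwMS, so the completer group in Section 3.2 is undefined in the data and non-use cannot be separated quantitatively from lack of effect.

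This affects one of five objectives. It should be corrected before PwMS are enrolled, because an SAP can refine definitions and models but cannot recover data that were not collected.

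The conclusion rests on three assumptions: that the fidelity scales are those of Section 3.2; that the long-term outcomes in Objective 5 are the month-6 primary outcomes; and that no usage data are planned beyond Table 3 and Section 9.1. Both parts of the fix also need MS-WIS at month 6. The text of Section 7.4 schedules it, but Table 3 as available to me marks MS-WIS only at screening and baseline, so the two should be checked against each other.

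**What to change.** Split Objective 5 in two.

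- **(a) Mechanism.** Does change from baseline to week 8 in psychological flexibility, resilience and self-efficacy predict month-6 MS-WIS, adjusted for baseline?
- **(b) Fidelity.** Do delivery and use of READY predict month-6 MS-WIS, adjusted for baseline?

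For (b), define fidelity separately from the outcomes and add these rows to Table 3:

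- modules completed, from a platform export or, if there is none, a self-report item at T2 and T3;
- booster module done, at T3;
- week-3 call held, yes or no.

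Link the existing competency score of the supporting HCP to each participant, bearing in mind that it varies only between HCPs. List the new data in Section 9.1, name the variables in Section 8.2, and use the module count to define the completers in Section 3.2. Report (a) and (b) as associations, stating that use is self-selected and that there is no comparison arm.

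The cost is new objective wording, a data export or one or two extra questionnaire items, and one yes/no field for the HCP. Recruitment stays at 250.
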